NCT02753816

Document Date: 07/10/2018

1. TXA Protocol Title: The effect of tranexamic acid on blood loss and transfusion rates in burn wound surgery – A randomized, double-blinded placebo-controlled trial.

2. Version Date: 7/10/18

3. Objectives:

- To determine the impact of perioperative administration of tranexamic acid on intra-operative blood loss and post-operative transfusion rates in burn wound surgery.

4. Background:

An estimated 40,000 patients were hospitalized for burn related injuries in 2014.¹ Many of these patients required surgical excision and grafting. Early excision of burn eschar has been shown to reduce mortality, hospital stay, and time away from work. However, intraoperative blood loss and blood product transfusion rates have been shown to be higher.^{2,3} Tangential excision of burns often causes large losses of blood, which have been estimated between 0.4 ml/cm² to 0.75 ml/cm² of debridement depending on timing of excision.⁴ There are many techniques that have been described to help reduce the loss of blood in burn surgery. These include timing of excision, maintaining euthermia, extremity tourniquet control, dilute epinephrine tumescent infiltration, and topical application of epinephrine and thrombin.^{5,6}

Tranexamic acid (TXA) has been used as an adjuvant to reduce bleeding since the 1960's.⁷ TXA acts by competitively binding to plasminogen leading to inhibition of its activation to plasmin. This is thought to inhibit fibrinolysis, maintain formed clot, and decrease perioperative bleeding.⁸

Topical and intravenous uses of TXA have been studied in a variety of surgical specialties, including orthopedic surgery,⁹ oral surgery,¹⁰ cardiovascular surgery,¹¹ trauma,¹² as well as gynecology.⁷ Impact on blood loss and decreased transfusion needs have been promising. Very little data exist on the use of TXA in burn surgery with only one case report and one prospective trial published.^{13,14} Although a small sample size was used, results were encouraging for decreasing intraoperative blood loss. The effect on perioperative blood transfusion was not addressed in this study.

Due to inhibition of fibrinolysis, a theoretical risk of venous thromboembolic (VTE) events is at the forefront for concern. Numerous studies have shown no increase in VTE events with perioperative use of TXA.^{9,15} Although the reasons are unclear, incidence of VTE within the burn population are quite low (0.8%) compared to many inpatient populations.¹⁶

We believe TXA has the potential to assist in perioperative control of hemorrhage during burn excision surgery leading to decreased blood loss and smaller transfusion rates. These potential improvements in care may translate into decreased surgical complications and a potential reduction in hospital stay and overall costs.

5. Setting of the Research:

Spectrum Health Butterworth Campus

6. Resources Available to Conduct this Research:

The Spectrum Health Regional Burn Center admits nearly 120 patients each year. Many of these patients require surgical management of their sustained injuries. Study personnel will

include attending burn surgeons and surgical residents with experience in surgical research and knowledge of surgical outcome measures. In addition, the Spectrum Health Office of Clinical Research Operations (OCRO) staff will assist with the informed consent process and subject enrollment, data collection and management, Institutional Review Board (IRB) communication and continuing renewal submission, ongoing subject management, and maintenance of the regulatory files and essential documentation for the study.

7. Study Design:

a. Recruitment Methods

Potential subjects will be recruited during the preoperative period for a planned procedure with any of the burn attending surgeons. A member of the Spectrum Health OCRO will obtain informed consent. This will take place in a private consultation room to ensure privacy and should take approximately 45-60 minutes. In order to minimize coercion, it will be made very clear to patients that their participation is strictly voluntary and that choosing not to participate will in no way affect their care at Spectrum Health.

Study Subjects

Potential subjects include all patients scheduled to undergo burn excision surgery with a deep partial or full thickness burn wound area of at least 350 cm² that meet all of the inclusion criteria, and none of the exclusion criteria. For a procedure to be included within the study, 96 hours must have elapsed since the previous procedure in which the patient was randomized to drug or placebo. If the patient has undergone a procedure outside the scope of this study, the 96-hour waiting period does not apply.

i. Inclusion Criteria

- Subjects undergoing burn excision surgery for standard of care purposes (to include: greater than or equal to 350 cm² of full thickness or deep partial thickness burns)
- Male or female \geq 18 years of age
- Subject or subject's medical decision maker agrees to participate in this study and provides informed consent

ii. Exclusion Criteria

- Subjects with a history of hypercoagulopathy, deep vein thrombosis or pulmonary embolism
- Baseline creatinine level greater than 2.83 mg/dL
- Subjects with known hypersensitivity to tranexamic acid
- Patients with acquired defective color vision
- Patients with subarachnoid hemorrhage
- Children
- Pregnant women
- Prisoners

b. Study Endpoints

The primary outcome measures will be operative blood loss (measured and calculated) and red blood cell transfusion rates in subjects undergoing the eligible procedures. Secondary outcome measures will include total hospital length of stay, wound complication, transfusion reactions, and skin graft survival.

c. Procedures Involved in the Research

The study design will be a randomized, double-blinded, placebo-controlled trial, with the randomization to occur on a per procedure basis. Following satisfaction of inclusion/exclusion criteria and enrollment into the study by the Spectrum Health OCRO research staff, the subject and each procedure the patient undergoes will be assigned a study number. A single consent will be obtained for randomization of each procedure that a patient may undergo meeting inclusion criteria for the study. A single study participant could potentially be randomized to both treatments of the study if that participant undergoes two or more procedures. Each procedure a participating subject undergoes will be randomized based on a predetermined randomization schedule, created by an independent statistician at Grand Rapids Medical Education Partners (GRMEP) research department. The randomization schedule will be held by the pharmacists and checked prior to each procedure to determine the appropriate treatment (placebo or TXA). Surgical timing will be coordinated with the OCRO. The study participants will receive preoperative intravenous TXA or Normosol as placebo treatment. The preparation will be indistinguishable by nursing, surgical, or anesthesia staff. The TXA procedures will receive a 1000 mg dose immediately preceding surgical incision administered by the anesthesia provider, while the placebo procedures will receive an equivalent volume of Normosol. The dose will be administered via intravenous piggyback over 15 minutes. Operative details will be recorded including procedure performed, IV fluids received, estimated blood loss, lowest recorded body temperature, and transfused blood products. Perioperative hemoglobin level data will also be collected. Standard daily laboratory measurements will continue unless clinical conditions necessitate more frequent monitoring, per standard practice. Transfusion will take place for hemoglobin levels < 7.0 g/dL or hemoglobin level < 10 g/dL with clinical symptoms indicating need for transfusion, per standard practice. Final decision on transfusion will be made according to the staff surgeon's discretion.

It is anticipated that each patient will receive an average of three major surgical procedures during the treatment of their burn injury. The number of procedures may range from a single procedure to greater than 6 procedures for an individual patient depending on the extent of their injury. The time between subsequent procedures typically ranges from ten days to several weeks. Prior to each procedure, the patient will be re-randomized to receive TXA or placebo.

Data to be recorded includes patient demographics (age, sex, height, weight), burn injury characteristics (total body surface area, location, depth of burn), hospital admission date, hospital discharge date, past medical history, past surgical history, medications, and laboratory values. Data from operative records will include procedure date, procedure performed, wound measurements, lowest body temperature, operative blood loss, operative time, amount of fluid received, and intraoperative transfusion requirements. Postoperative data to be collected includes hemoglobin and hematocrit levels, transfusion requirements, surgical complications, skin graft survival (%), thromboembolic events, and length of hospital stay.

d. Data Management

The Spectrum Health OCRO research staff will collect outcome data at the time of each surgical procedure. Data will be stored in a password-protected REDCap

database. The OCRO will also keep a secure record of the procedures randomized to the TXA and placebo arms, which will be blinded from the study personnel.

e. Provisions to Monitor the Data for the Safety of Subjects

Adverse events including infections, allergic reactions, graft loss, respiratory failure, anaphylaxis, thromboembolic events and development of acute renal failure will be monitored and recorded at the time of occurrence by the Spectrum Health OCRO research staff. In the event an increased number of unanticipated events occur, the study will be temporarily stopped pending review. A review of unblinded data will be performed by an independent clinician and statistician at Grand Rapids Medical Education Partners to determine the need to discontinue or resume the study. If a significant increase in adverse events is noted in the treatment arm related to the study drug, the trial will be terminated. Decisions resulting from the review will be discussed with the primary investigator.

Interim reviews of unblinded data for statistically significant findings will be performed by an independent clinician, pharmacist, and statistician after the first 80 procedures have been completed. Findings will be reviewed with the investigators, and decisions will be made as to whether or not the research study continues. These interim reviews and outcomes will be reported to the IRB.

f. Withdrawal of Subjects

Subjects will be withdrawn from the study if they experience an adverse drug reaction defined as anaphylaxis. Other potential side effects such as nausea, vomiting, or diarrhea will be treated symptomatically per standard of care. If refractory to standard treatment for these side effects, subjects will be withdrawn from the study. Subjects experiencing any thrombotic event prior to completion of study drug dosing schedule will be withdrawn from study. Subjects may choose at any time to voluntarily withdraw from the study. If subjects choose to withdraw, No further data will be collected. Data already collected will be included in the study.

The primary investigator may remove a subject at any time from this research study if it is felt to be in the best interest of the subject.

8. Statistical Plan

a. Sample Size Determination

The primary outcome variable for the study is transfusion following a procedure. The analysis will be performed using generalized estimating equations (GEEs), as each individual may have multiple surgical procedures that may be randomized to either the control or TXA treatment prior to EACH procedure. An initial assessment for sample size for a McNemar test, assuming that the transfusion rate following a control procedure is 50%, the rate following a TXA procedure is 30%, $\alpha = 0.05$ and $\beta = 0.20$, indicates that 61 subjects would be needed. The control transfusion rate is based upon previous data at Spectrum Health, while the difference of 20 percentage points is based upon our estimate of what constitutes a clinically important effect. Due to the use of GEE for the analysis, a correction factor is needed.¹⁷ From previous data from the Spectrum Health Burn Unit, we assume that there will be three procedures per patient. If we further assume that the intraclass correlation coefficient = 0.8 (postulated correlation of repeated measurements), we will be able to show a statistically significant effect with 53 subjects. With an average of 3 procedures per patient, the total procedures will be 159.

b. **Statistical Methods**

Summary statistics will be calculated. Quantitative data will be expressed as the mean±SEM and nominal data will be expressed as a percentage. Comparisons between groups for quantitative variables will be performed using the t-test. Nominal variables will be evaluated using the χ^2 test. The relationship between TXA administration and transfusion will be determined using GEE. Significance will be assessed at $p<0.05$. Analyses will be performed using intention to treat.

9. Risks to Subjects

TXA is an FDA approved medication. The safety of TXA has been demonstrated in a meta-analysis of the off-label use of TXA in the perioperative period. A theoretical risk of thromboembolic events exists, though no significant adverse outcomes have been reported with the proposed dosing schedule. Reported side effects include nausea, vomiting, diarrhea, and dizziness. Uncommon side effects include allergic dermatitis, giddiness, and hypotension. Rare side effects include blood clots, convulsions, and visual changes.

10. Potential Benefits to Subjects

Potential benefits include decreased surgical blood loss resulting in decreased transfusion requirements. Transfusion of packed red blood cells has been associated with numerous potential adverse events. In addition, decreased overall hospital cost may occur if the study subjects experience decreased complication rates.

11. Provisions to Protect the Privacy Interests of Subjects

The study, potential risks and benefits of treatment will be discussed extensively with each potential subject preoperatively in a private space. Any questions they have will be answered accordingly. Reported data will not contain identifiable information. Patient consent and all other research related activities will take place in a private exam room.

12. Provisions to Maintain the Confidentiality of Data

Identifiable study data will be kept in a secure password-protected file or locked cabinets by the Spectrum Health OCRO. The Spectrum Health OCRO will have record of the randomization of each individual subject stored in a controlled, secure area.

13. Medical Care and Compensation for Injury

Any medical or surgical complications experienced relative to this research will be treated in accordance with current standards of care. No study funds have been set aside to compensate subjects for injury.

14. Cost to Subjects

Study drug, placebo, and preparation/administration will be paid for by funds allocated to the study, and not billed to the subjects. All other aspects of the subject's care are considered standard of care, and will be billed to the patient and/or their insurance company.

15. Consent Process

Eligible subjects will be recruited during their inpatient stay. The potential risks and benefits of the study will be discussed in detail by a member of the Spectrum Health OCRO in a private space. All subjects will be ensured adequate time to read the research informed consent form, and all questions will be answered to their satisfaction. Subjects will be informed that the research is a voluntary option.

16. Vulnerable Populations

Patients with diminished decision-making will be included within the study as the possibility of direct benefit outweighs the risks of the study drug. A patient will be considered to have diminished decision-making capacity if they have previously been assigned a guardian in-charge of their medical decision making or if the patient's medical condition interferes with their ability to communicate effectively or understand the medical decisions presented to them. If a patient is unable to make medical decisions due to circumstances surrounding their sustained injuries or they have an assigned legal guardian, patient recruitment will be done through the legally authorized representative. Written consent will be obtained prior to the first surgical procedure. If the patient's decision-making capacity becomes reestablished the patient will be reconcented through the standard informed consent process.

17. Sharing of Results with Subjects

At this time there are no plans to share study results with study participants.

18. References

1. American Burn Association. Burn incidence fact sheet.
http://www.ameriburn.org/resources_factsheet.php. Accessed May 20, 2015.

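### Section 8b adjusts neither blood loss nor transfusion for timing of excision or wound area, although the protocol's own figures make both prognostic; the cost is some precision, not bias

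*Combined protocol and SAP*

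**What the plan says.** Section 4 (Background) states that blood losses from tangential excision have been "estimated between 0.4 ml/cm² to 0.75 ml/cm² of debridement depending on timing of excision". It puts timing first among the techniques that reduce loss: "These include timing of excision, maintaining euthermia, extremity tourniquet control". Because the figure is per cm², wound area matters as well. Section 7a requires a "deep partial or full thickness burn wound area of at least 350 cm²" and states no upper limit.

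Section 7b names as primary outcomes "operative blood loss (measured and calculated) and red blood cell transfusion rates".

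Section 7c lists "burn injury characteristics (total body surface area, location, depth of burn), hospital admission date, hospital discharge date" among the data to be recorded, and adds: "Data from operative records will include procedure date, procedure performed, wound measurements". No date of burn is named. On spacing it says: "The time between subsequent procedures typically ranges from ten days to several weeks", with a new randomization before each procedure. It describes no stratification.

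Section 8b assigns t-tests to quantitative variables and says of transfusion: "The relationship between TXA administration and transfusion will be determined using GEE". It names no covariate for any analysis.

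**The concern.** By the sponsor's own figures, two features known before incision predict blood loss, and plausibly transfusion: how large the wound is and when it is excised. The planned data yield both, at least approximately, but neither enters an analysis.

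Clustering by patient does not recover the loss. Operations ten days to several weeks apart fall at different times after injury, so timing varies within a patient as well as between patients. The variation that timing and area explain therefore stays in the error term of the blood-loss comparison and goes unused in the transfusion GEE. At stake is precision that would need no extra patients in a trial of 53 subjects.

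**Working it through.** **The plan's own figures**
- Timing (section 4): 0.75 / 0.40 = 1.875. At the 350 cm² entry minimum, this is 140 ml against 262.5 ml, a difference of 122.5 ml.
- Sample size (section 8a): 61 × [1 + (3 − 1) × 0.8] / 3 = 52.87, rounded up to 53 subjects; 53 × 3 = 159 procedures. The planning rates of 50% and 30% are marginal, so variation in timing and area is already inside them.

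**Blood loss: share of log-scale variance due to timing**

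The documents give no SD and no timing distribution. Assumptions: residual log-SD 0.5 to 0.7 (variance 0.25 to 0.49), log-area SD 0.5 to 0.8 (variance 0.25 to 0.64), and timing independent of area.

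ln(1.875) = 0.629, and its square is 0.395. Timing variance is then:
- even spread on the log scale between the two figures: 0.395 / 12 = 0.033
- all procedures at the two extremes: 0.395 × p(1 − p) = 0.099 for p = 1/2, and 0.088 for p = 1/3

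Share = timing variance / (timing variance + residual variance, plus area variance if area is not adjusted for).

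| Timing | Area adjusted | Area not adjusted |
|---|---|---|
| Even spread | 0.033/0.523 = 6% to 0.033/0.283 = 12% | 0.033/1.163 = 3% to 0.033/0.533 = 6% |
| Two extremes | 0.088/0.578 = 15% to 0.099/0.349 = 28% | 0.088/1.218 = 7% to 0.099/0.599 = 16.5% |

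The area-adjusted, even-spread share narrows a confidence interval by about 1 − √0.94 = 3% to 1 − √0.88 = 6%. On these assumptions area is the larger factor: its smallest variance, 0.25, is about 2.5 times the largest timing variance, 0.099.

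**Transfusion: simulated GEE power**

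53 patients, mean of 3 procedures, small-sample-corrected test, 2,000 trials per row. The shares of transfusion propensity are assumed.

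| Area / timing share | Unadjusted | Timing | Timing and area |
|---|---|---|---|
| 10% / 3% | 77.0% | 77.7% (+0.7) | 78.9% (+1.9) |
| 20% / 5% | 76.0% | 77.8% (+1.8) | 81.0% (+5.0) |
| 30% / 7% | 75.6% | 77.8% (+2.2) | 83.2% (+7.6) |

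The Monte Carlo standard error of each power is about √(0.77 × 0.23 / 2,000) = 0.9 points, so the smallest gain is within noise.

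As a sensitivity check, transfusion was modelled as a threshold on log blood loss (marginal rates 50% and 30%, total CV 0.5 to 1.0, latent intraclass correlation 0.4 or 0.8, 600 runs each). Adjusting for timing alone then gained about 1 to 6 points with an even spread and about 5 to 16 with procedures at the extremes. I treat this as the optimistic end: section 7c bases transfusion on hemoglobin, symptoms and the surgeon's discretion, not on blood loss alone.

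**The case against.** Four stronger readings are tempting, and the documents do not support them.

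- A reader might infer that timing cannot be analysed because the burn date is not collected. The date is unlisted, not ruled out, since the list in 7c is not presented as exhaustive. Days from admission to procedure can be derived from listed dates. That proxy is weaker where admission was delayed or by transfer.
- A reader might infer bias from a chance imbalance of early excisions. Each procedure is randomized, so imbalance is random error that the unadjusted standard error already covers. Counting it beside lost precision counts one cost twice.
- A reader might take 15-28% as the loss under the plan. It needs every procedure at one of the two extremes and area already removed. The planned t-test does not remove area, and the protocol gives a range, not two groups.
- A reader might infer that the sample size is wrong. With marginal planning rates, this point does not touch the 53.

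Two further objections stand in part. The range is a cited background estimate, not site data, and even its direction is unclear: section 4 says blood loss has been higher with early excision, while the title of the study cited for the range says early excision reduces it. Any assumed shape for the timing effect is therefore a guess. With per-procedure randomization, a poor shape forfeits some gain but does not bias the treatment comparison. Also, most of the transfusion gain comes from area, so timing alone is a weak case. Both covariates belong in the fix.

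**Conclusion.** The point holds as a modest, optional improvement. Section 8b pre-specifies no covariate, although section 4 makes timing and area prognostic and section 7c lists the data needed to use them.

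The consequence is lost precision only. For blood loss, timing accounts for about 3-12% of log-scale variance if evenly spread and about 7-28% at the extremes; the lower end of each range applies while area stays unadjusted. For transfusion, the main simulation gives about 1-2 power points from timing and about 2-8 from timing plus area. All of these sizes rest on assumed residual, area and timing distributions that the documents do not supply. The factual core, namely the 1.875-fold range, the listed data and the absence of covariates, does not.

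**What to change.** In section 8b, pre-specify two covariates for both primary outcomes:
- pre-operative wound area; and
- time to procedure: days from admission to procedure, or from burn if the burn date is added to the list in 7c.

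Fit them in the transfusion GEE and in a blood-loss model that accounts for clustering by patient and replaces the t-test. Use only values known before incision. Area actually excised is settled during surgery and should not be the covariate; eligibility already requires the wound area to be assessed. Fix the functional form of each covariate before unblinding. A separate first-versus-later term is optional, because it overlaps with time to procedure.

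Report a standardized risk difference for transfusion. In a logistic GEE, adjustment turns the marginal odds ratio into a conditional one; standardizing keeps the result comparable with the 20-point target in section 8a.

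Cost: two model terms, a standardization step with its own variance estimate on about 53 clusters, and optionally one data field. No extra patients or procedures are needed.

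### Planned tourniquet and tumescence use is not recorded, so the blood-loss comparison gives up some precision if that use varies between procedures

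*Combined protocol and SAP*

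**What the plan says.** Section 4 (Background) introduces the topic with "There are many techniques that have been described to help reduce the loss of blood in burn surgery" and then names five: timing of excision, keeping the patient warm, and "extremity tourniquet control, dilute epinephrine tumescent infiltration, and topical application of epinephrine and thrombin".

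Section 7b sets the endpoints: "The primary outcome measures will be operative blood loss (measured and calculated) and red blood cell transfusion rates".

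Section 7c gives two lists of operative data. The first reads "Operative details will be recorded including procedure performed, IV fluids received, estimated blood loss, lowest recorded body temperature, and transfused blood products". The second reads "Data from operative records will include procedure date, procedure performed, wound measurements, lowest body temperature, operative blood loss, operative time, amount of fluid received", and ends with intraoperative transfusion. Neither names tourniquet, tumescent infiltration or topical hemostatics. The nearest general item is in the patient-history part of 7c: "past medical history, past surgical history, medications, and laboratory values". Burn location is listed there too, with the injury characteristics.

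Section 7a allows recruitment for "a planned procedure with any of the burn attending surgeons", and no section sets a common approach to hemostasis. Section 7c states that nursing, surgical and anesthesia staff cannot tell the two preparations apart. Section 8b compares quantitative variables by t-test and keeps GEE for transfusion. Section 8a bases the sample size on transfusion alone.

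**The concern.** The protocol itself treats these three measures as influences on one of its primary outcomes, then plans no item for them. They can act in two ways.

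- **Planned use.** A tourniquet or tumescence decided before the infusion is a baseline predictor of blood loss. Randomization balances it on average, but whatever variance it causes stays in the unadjusted comparison.
- **Bleeding-driven use.** A topical agent started because the field is bleeding comes after randomization. If TXA works, placebo procedures may attract it more often, and the absolute difference in blood loss narrows.

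At stake are the precision of the blood-loss estimate and the reading of a small absolute difference. Without records by arm, one cannot see whether the arms received different amounts of added hemostasis.

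**Working it through.** **1. The plan's own figure.** Section 8a starts from 61 subjects and uses 3 procedures per patient and an intraclass correlation of 0.8. The correction is 61 × [1 + (3 − 1) × 0.8] / 3 = 61 × 0.8667 = 52.87, rounded up to 53; 53 × 3 = 159 procedures. This agrees with the plan, and nothing here disputes it. It concerns transfusion. No mean, standard deviation or target difference is given for blood loss, so power for that outcome cannot be derived from the documents.

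**2. Which of the five techniques leave a trace in the data.**

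| Technique (section 4) | Item in section 7c |
|---|---|
| Body temperature | Yes, lowest recorded value |
| Timing of excision | In part: admission and procedure dates, but no injury date is listed |
| Tourniquet | None named |
| Epinephrine tumescence | None named |
| Topical epinephrine or thrombin | None named |

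**3. Planned use: precision available.** Let R² be the share of blood-loss variance explained by planned tourniquet and tumescence beyond burn location and wound measurements. All values of R² are assumed. The standard error after adjustment is about √(1 − R²) times the one before, and the equivalent gain in procedures is 1/(1 − R²).

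| Assumed R² | √(1 − R²) | Fall in standard error | 1/(1 − R²) |
|---|---|---|---|
| 0.10 | 0.949 | 5% | 1.11 |
| 0.20 | 0.894 | 11% | 1.25 |
| 0.30 | 0.837 | 16% | 1.43 |

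If planned use hardly varies, or follows almost entirely from burn location, R² is near zero and so is the gain.

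**4. Planned use: illustration.** Take log-normal blood loss with log-scale standard deviation 0.5 and a true TXA reduction of 25%. Let planned measures be used in a random half of procedures and cut loss by 30%, 50% or 70%. All of these inputs are assumed. The relative reduction stays at 25%. The standardised difference falls from 0.53 to 0.50, 0.43 and 0.35, because mixing procedures with and without the measure widens the spread.

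**5. Bleeding-driven use: illustration.** Use the same model, but let hemostasis remove 30%, 50% or 70% of any loss above the control median.

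| Share of excess removed | Absolute difference (0.284 without hemostasis) | Fall | Relative reduction (true 25%) | Standardised difference (0.53 without) |
|---|---|---|---|---|
| 30% | 0.234 | 18% | 22% | 0.55 |
| 50% | 0.200 | 30% | 20% | 0.57 |
| 70% | 0.167 | 41% | 18% | 0.57 |

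The absolute difference shrinks, but the spread shrinks with it, and the standardised difference does not fall. In this model the narrowing costs no power.

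**The case against.** A reader might infer that bleeding-driven hemostasis can hide a TXA effect. The documents do not support that. Surgical staff are blinded and each procedure is randomized, so no false effect arises. When the rescue mechanism is modelled, the standardised difference does not fall. A smaller difference with usual hemostasis in place is also a legitimate intention-to-treat effect: that of TXA added to usual care, in surgery that section 7a describes as standard of care. This part of the objection stands.

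A reader might also infer that these measures vary freely by surgeon and procedure. The documents are silent: section 4 says only that the techniques have been described, and nothing shows how often or how variably this single center uses them. So the precision argument is conditional.

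Nor can one say that nothing will be recorded. Both lists are open-ended, the case-report form is not part of the documents, and the items for procedure performed or medications could catch some use. Burn location and wound measurements are recorded and probably carry part of the same information. This limits the gain. It does not remove the gap, because no item is specified and an incidental mention would not reliably separate planned from bleeding-driven use.

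Finally, it is tempting to say that infiltrated fluid inflates measured loss and should be subtracted. Section 7b does not say how loss is measured. If only part of the infiltrate is recovered, full subtraction would over-correct.

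**Conclusion.** The point holds as an optional gain in precision. Three measures that the protocol names as reducing blood loss have no specified data item, and a primary outcome that they may influence is compared without adjustment. Validity is not threatened.

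The loss is one of precision, and it exists only if planned use varies between procedures. For an assumed incremental R² of 10-30%, the standard error would fall by 5-16%. That range rests on no figure in the documents, and the true increment may be smaller. A second, qualitative cost is that a small absolute difference is harder to interpret when hemostasis by arm is unknown. Loss of power from bleeding-driven use is not shown.

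**What to change.** Add per-procedure REDCap items:

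- tourniquet planned (yes/no) and tumescence planned (yes/no), both entered before the study infusion starts;
- volume infiltrated;
- topical hemostatic used, and whether it was started for bleeding after incision.

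In section 8b, replace the t-test for blood loss with a model that allows for repeated procedures per patient. Include the two pre-infusion items together with the burn location and wound area already recorded.

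Report bleeding-driven topical use by arm descriptively. It follows randomization, so it should never be a covariate, and reporting it helps interpretation without restoring a narrowed difference. Do not subtract infiltrated volume automatically; use it only in a sensitivity analysis, and only if measured loss comes from collected fluid.

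Surgical technique is not restricted. The cost is a short pre-infusion entry by the surgical team, a few extra fields and one changed model specification. Whether use was planned or reactive is hard to reconstruct afterwards, so it has to be captured at the time.
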